9.2. Sample Size and Power Considerations

The study aims to detect potential beneficial effects in deteriorating clinical signs and symptoms. Based on previous studies in patients with HD, the UHDRS-TMS has been shown to be one of the more sensitive clinical measures to detect decline in symptoms of HD. It is estimated that approximately 100 patients per arm will enable a power of 80% to detect a beneficial effect compared to placebo, of 2.5 points or more in the change from baseline in UHDRS-TMS of an active laquinimod arm, assuming SD of 6.2 and type I error of 5%.

As the intention is to investigate laquinimod as a treatment with the potential to slow disease progression and prohibit neuronal death in the CNS, the study should also be sized to be able to detect changes in brain atrophy rate after treatment with laquinimod. One of the most sensitive measures to detect brain atrophy over time in patients with HD is change in the caudate volume.

It is estimated that approximately 100 patients per arm will enable a power of 80% to detect a beneficial effect of 0.95 (30% of the estimated decline in placebo) or more in the percent change from baseline in caudate brain atrophy of an active laquinimod arm compared to placebo, assuming SD of 2.36 and type I error of 5%.

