9.6. Efficacy Analyses

9.6.1. Efficacy Variables

9.6.1.1. Primary Efficacy Variable and Endpoint

The primary efficacy variable and endpoint for this study is the change from baseline in the UHDRS-TMS (defined as the sum of the scores of all UHDRS-TMS subitems) at Month 12/ ET (evaluated at baseline and Months 1, 3, 6 and 12)

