9.6.2.1. Primary Efficacy Endpoint Analysis

The change from baseline in UHDRS-TMS, will be analyzed using a Repeated Measures model (SAS® MIXED procedure with REPEATED sub-command). The model will include the following fixed effects: categorical week in trial by treatment interaction, center, and UHDRS-TMS at baseline. The unstructured covariance matrix for repeated observations within patients will be used. In case that the model will not converge, the Maximum-Likelihood (ML) estimation method will be used instead of the default Restricted ML (REML). If the model still does not converge then a simpler covariance structures with less parameters will be used, according to the following order: Heterogeneous Autoregressive(1) [ARH(1)], Heterogeneous Compound Symmetry (CSH), Autoregressive(1) [AR(1)], and Compound Symmetry (CS). The estimated mean changes from baseline at the Month 12//Early Termination visit will be compared between the active treatment arms and the placebo arm.

The Hochberg's Step-Up method for multiple comparisons between treatment arms will be used to control inflation in type I error rate.

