9.6.2.2. Secondary Efficacy Endpoints Analyses

According to the hierarchical method to control inflation in type I error rate for multiple endpoints, any statistically significant dose that will be observed in the primary analysis will continue to be tested for the secondary endpoints at an alpha level of 5%, according to the secondary endpoints order.

The secondary efficacy endpoints: change from baseline in HD-CAB total score and change from baseline in UHDRS- TFC, will be analyzed in the same way as the primary efficacy endpoint except that the efficacy endpoint evaluation at baseline will be included in the model instead of baseline UHDRS-TMS.

The CIBIC-Plus will be analyzed in the same way as the primary efficacy endpoint except that the baseline CIBIS (Clinician's Interview-Based Impression of Severity) will be included in the model as the efficacy measure at baseline.

The percent change from baseline to Month 12/Early Termination in caudate volume will be analyzed using an Analysis Of Covariance (ANCOVA) model (SAS® MIXED procedure). The model will include the following fixed effects: treatment, center, and caudate volume at baseline.

The estimated means at the Month 12 visit will be compared between the active treatment arms and the placebo arm. Early terminated patient observation will have their Last Observation Carried Forward (LOCF).

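### The repeated-measures model fits one baseline slope for all visits, so precision at Month 12 may be lost if that slope changes over time; adding baseline-by-week costs almost nothing

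*Protocol*

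**What the plan says.** Section 9.6.2.1 analyses change from baseline in UHDRS-TMS with a repeated-measures model whose fixed effects are "categorical week in trial by treatment interaction, center, and UHDRS-TMS at baseline". The synopsis lists the same terms. Baseline appears once, as a main effect, and nothing else in the protocol adds a baseline-by-week term. On covariance: "The unstructured covariance matrix for repeated observations within patients will be used". A fallback order is given in case the model does not converge.

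The outcome is "evaluated at baseline and Months 1, 3, 6 and 12", so four post-baseline visits share the model. The test uses the last of them: "The estimated mean changes from baseline at the Month 12//Early Termination visit will be compared between the active treatment arms and the placebo arm".

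Section 9.6.2.2 applies the same model to HD-CAB total score and TFC, "except that the efficacy endpoint evaluation at baseline will be included in the model instead of baseline UHDRS-TMS". It treats CIBIC-Plus likewise, with baseline CIBIS as covariate. These three endpoints have two post-baseline visits, Months 6 and 12. Section 9.6.2.4 plans no sensitivity analyses.

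**The concern.** A baseline main effect in a repeated-measures model means one regression coefficient for all visits. The relation between baseline score and change need not be the same after one month as after twelve in a progressive disease. If it differs, the common coefficient is a compromise that need not suit Month 12, the only visit tested. Variance that baseline could have explained there then stays in the treatment contrast.

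The list of terms is not something the protocol leaves open. It defers imputation rules and centre pooling to the statistical analysis plan, but it fixes the model terms itself, down to the order of covariance fallbacks. What is at stake is efficiency, and how well chance baseline imbalance at Month 12 is corrected.

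**Working it through.** **1. The plan's own figure.** Section 9.2 says that "approximately 100 patients per arm will enable a power of 80" per cent for "2.5 points or more in the change from baseline in UHDRS-TMS", "assuming SD of 6.2 and type I error of 5" per cent. Sidedness is not stated and is taken as two-sided.

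- n per arm = 2 × ((1.960 + 0.842) × 6.2 / 2.5)² = 96.5, so 97.
- Power at 100 per arm: 2.5 / (6.2 × √(2/100)) = 2.851; Φ(2.851 − 1.960) = 81.4%. The t-test version gives 81.0%.

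The figure reproduces. It uses SD 6.2 for change and takes no credit for baseline adjustment.

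**2. What sets the common slope.** With complete data and unstructured residual covariance S over the four visits, and visit-specific slopes b, the common slope is

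c = (1′S⁻¹b) / (1′S⁻¹1),

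a weighted combination of the visit slopes. The weights depend only on S. The protocol gives the SD at Month 12 (6.2) and nothing on earlier visits or correlations, so these inputs are assumed:

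| Residual SDs, Months 1/3/6/12 | Correlation | Weight of Month 1 | Weight of Month 12 |
|---|---|---|---|
| 4 / 5 / 5.6 / 6.2 | 0.6 | 76% | −5% |
| 5 / 5.5 / 5.9 / 6.2 | 0.6 | 50% | 7% |
| 6.2 at all visits | 0.6 | 25% | 25% |

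If variance grows with time, the adjustment at Month 12 is mostly the Month 1 slope. Even with equal SDs, three quarters of the weight lies on earlier visits.

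**3. Cost at Month 12.** Relative to visit-specific slopes, the variance of the Month 12 contrast is multiplied by

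1 + (b₁₂ − c)² × Var(baseline) / Var(residual at Month 12).

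Assumed ranges: baseline SD 10 to 15; correlation 0.6 to 0.8; SDs of change 4/5/5.6/6.2, 3.5/4.2/5/6.2 or 6.2 throughout.

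Two worked cases use the larger-drift pattern, in which b₁₂ = 0 and the Month 12 residual variance is 6.2² = 38.44:

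- Flat SDs, correlation 0.6, baseline SD 10: c = −0.059, so 1 + 0.059² × 100 / 38.44 = 1.009.
- SDs 3.5/4.2/5/6.2, correlation 0.8, baseline SD 15: c = −0.136, so 1 + 0.136² × 225 / 38.44 = 1.108.

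| Assumed slopes, Months 1/3/6/12 | Extra variance at Month 12 | Power difference between the two models |
|---|---|---|
| −0.10 at all visits | 0% | 0 |
| Mild drift: −0.05 / −0.06 / −0.08 / −0.10 | 0.2 to 2.9% | 0.1 to 1.0 points |
| Larger drift: −0.10 / −0.08 / −0.05 / 0 | 0.9 to 10.8% | 0.3 to 4.1 points |

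**4. Check by simulation.** With 3,000 replicates, three arms of 100, baseline SD 12, correlation 0.6 and SDs of change 4/5/5.6/6.2, the ratios of Month 12 variance (common over visit-specific slopes) were 1.000, 1.011 and 1.033 for the three rows. The formula gives 1.000, 1.009 and 1.038 at the same inputs. Mean estimates under zero effect were close to zero in both models.

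**The case against.** The strongest reply is that nothing here is wrong. A single baseline term is a legitimate, unambiguous prespecified choice, stated identically in both places, and the stated power does not depend on it. That stands, and it is why this is a suggestion for improvement only.

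Several stronger readings are tempting, and the documents do not support them.

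- **That precision is lost.** This holds only if the slope changes, and nothing in the protocol shows that it does. Regression to the mean is not enough by itself: error in the baseline value enters every change score, Month 12 included. Drift requires 12-month progression to depend on baseline TMS within this early-disease population (TMS above 5, TFC at least 8).
- **That Month 12 is adjusted with a wrong coefficient, so the result is biased.** Under randomisation with complete data the contrast is unbiased with either model, and type I error is unaffected.
- **That the loss is large.** A slope reversing from −0.10 to +0.10 gives 3 to 45% extra variance under the same assumed inputs, with a simulated ratio of 1.160. No figure in the protocol suggests such a reversal.
- **That dropout makes it worse.** The calculations use complete data. Patients who stop drug are asked to keep attending (section 3.6.2), and those who withdraw have the Visit 8 assessments at their last visit (sections 3.1 and 4.3). How these data enter the Month 12 estimate is not settled in the protocol, so an effect through dropout is speculation.
- **That the secondary endpoints lose as much.** They have two post-baseline visits, CIBIC-Plus is itself a rating of change, and nothing was computed for them.

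**Conclusion.** The structural point holds: the model as written has one baseline slope for four visits, and under plausible covariance the earlier visits largely determine the adjustment at Month 12. The consequence is conditional. Under the assumed inputs, the Month 12 variance is 0% larger with equal slopes, about 0-3% larger with mild drift (at most 1 power point), and roughly 1-11% larger with larger drift (0.3 to 4.1 power points).

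All these figures rest on assumed slopes, baseline SD, correlations and earlier-visit SDs, and on complete data. The treatment estimate remains unbiased, type I error is unaffected, and the sample-size statement in section 9.2 is not called into question. This is a minor point, worth acting on only because the remedy is so cheap.

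**What to change.** Add the baseline UHDRS-TMS by week interaction to the fixed effects in section 9.6.2.1 and in the synopsis, so that each visit has its own baseline slope. With four post-baseline visits this is 3 further parameters in a trial of about 300 patients. For consistency, add the matching term to the repeated-measures models in section 9.6.2.2 (HD-CAB total score, TFC, and CIBIC-Plus with baseline CIBIS), at 1 parameter each. The size of any gain for those endpoints has not been computed.

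The change needs no new data, visits or patients. It should be made before unblinding.

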3.10. Time Schedule

The study started in Q4 2014 (first patient randomized) and is expected to be completed in Q1 2018 (last patient last visit).

As of 10 January 2016, treatment with laquinimod was discontinued for all patients in the 1.5 mg/day dose arm.

Approximately 300 patients (100 patients within each study arm), plus the 30 patients who were already randomized to the laquinimod 1.5 mg dose arm, from ~51 investigational centers in North America, Europe and Russia are planned to be enrolled in the study.

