9.6.2.3. Exploratory Efficacy Endpoints Analyses

The exploratory efficacy endpoints will be analyzed in the same way as the primary efficacy endpoint except that the efficacy endpoint evaluation at baseline will be included in the model instead of baseline UHDRS-TMS.

The change from baseline to Month 12/Early Termination of continuous efficacy endpoints that are measured at baseline and at month 12 only, will be analyzed using an ANCOVA model (SAS® MIXED procedure). The model will include the following fixed effects: treatment, center, and the efficacy measure at baseline. The estimated means at the Month 12 visit will be compared between the active treatment arms and the placebo arm. Early terminated patient observation will have their Last Observation Carried Forward (LOCF).

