9.6.2.5. Pooling of Small Centers

Centers with low number of patients will be pooled according to geographical region.

Details will be provided in the Statistical Analyses Plan (SAP).

The pooled center variable will be used in all statistical models that include center as covariate.

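### If the unstructured REML fit fails to converge, the plan switches straight to ML, which makes Month 12 standard errors slightly too small: a minor, conditional fault with a free fix

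*Protocol*

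**What the plan says.** Section 9.6.2.1 analyses change in UHDRS-TMS with a repeated-measures model whose fixed effects are "categorical week in trial by treatment interaction, center, and UHDRS-TMS at baseline". On the covariance it says: "The unstructured covariance matrix for repeated observations within patients will be used". The outcome is "evaluated at baseline and Months 1, 3, 6 and 12", so four post-baseline visits enter the model.

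The non-convergence rule is a fixed ladder. First, "the Maximum-Likelihood (ML) estimation method will be used instead of the default Restricted ML (REML". Then: "If the model still does not converge then a simpler covariance structures with less parameters will be used", in the order ARH(1), CSH, AR(1), CS. The text does not say whether REML returns once a simpler structure is in use, and it names no degrees-of-freedom method. The Synopsis repeats the ladder.

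Section 9.6.2.2 carries the method over to HD-CAB total, TFC and CIBIC-Plus. Section 9.6.2.3 does the same for the exploratory endpoints: "The exploratory efficacy endpoints will be analyzed in the same way as the primary efficacy endpoint".

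Two facts about centre bear on the size. Section 3.10 plans patients "from ~51 investigational centers in North America, Europe and Russia are planned to be enrolled in the study", and section 9.6.2.5 says "Centers with low number of patients will be pooled according to geographical region". It leaves the details to the SAP and uses the pooled variable in every model containing centre. Section 9.7 claims an experiment-wise type I error of 5%, and section 9.6.2.4 plans no sensitivity analysis.

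**The concern.** ML estimates the covariance as if the fixed effects were known. REML allows for the degrees of freedom they use. The shortfall under ML grows with the number of fixed effects, and here centre can contribute many.

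The ML step also keeps the unstructured matrix, with the same ten covariance parameters for four visits. It therefore gives up the correction without simplifying the structure that would usually cause the failure.

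What is at stake is the level of the primary test in the one situation the rule was written for. A prespecified fallback should not make that test anticonservative when a route that keeps REML is available.

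**Working it through.** **The plan's own figure.** Section 9.2 gives about 100 per arm for 80% power (difference 2.5, SD 6.2, 5%; two-sided assumed, as sidedness is not stated).

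- n = 2 × (1.960 + 0.842)² × 6.2² / 2.5² = 96.5, so 97 per arm.
- At 100 per arm, SE = 6.2 × √(2/100) = 0.877, and power = Φ(2.5/0.877 − 1.960) = 81.4%.

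The sample size reproduces. The concern is only with the fallback.

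**Inputs.** From the documents: about 300 patients in three arms (the 1.5 mg arm is descriptive only), four post-baseline visits, unstructured covariance, centre as a fixed effect, about 51 centres before pooling. Assumed: the number of pooled centre levels, shown as a range; visit SDs rising from 4.0 to 6.2; AR(1) correlation 0.6 or compound symmetry 0.8; no dropout or 15% monotone dropout.

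**Method.** Simulate data under no treatment effect and fit the same datasets by ML and by REML. Take r = SE(ML)/SE(REML) for the Month 12 contrast. The level implied by r is 2 × [1 − Φ(1.960 × r)].

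| Centre levels | r | 1.960 × r | Implied level |
|---|---|---|---|
| 12 | 0.987 | 1.935 | 5.3% |
| 20 | 0.982 | 1.925 | 5.4% |
| 45 | 0.964 | 1.889 | 5.9% |

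A separate set of runs agrees: r = 0.982-0.983 with 20 levels and 0.962-0.966 with 51 (5.8-5.9%), across both correlation patterns at 15% dropout and, for 51 levels, also without dropout.

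**Observed rejection rates** in those five settings, ML against REML on the same data: 5.3 v 4.5%, 5.4 v 4.5%, 5.8 v 5.0% (51 levels); 4.8 v 4.5%, 5.8 v 5.2% (20 levels). Each rests on 2,000-2,500 trials. ML was higher every time.

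**After Hochberg.** With correlation 0.5 between the two dose comparisons, the familywise level under the global null is about 4.8% with REML. Under ML it is about 5.3% with 20 levels and 5.8-5.9% with 51. Hochberg's small slack does not absorb the bias.

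**Why the effect is not larger.** In a single-visit ANCOVA the ratio would be √((n − p)/n). With 20 levels p = 3 + 19 + 1 = 23, giving √(277/300) = 0.961 and 6.0%. With 51 levels p = 54, giving √(246/300) = 0.906 and 7.6%. In the repeated-measures model one set of centre effects serves all four visits, so the loss at Month 12 is smaller.

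**Alternatives to ML.** An uncorrected sandwich standard error, simulated with complete data, was 0.981-0.984, 0.980-0.987 and 0.970-0.972 of the true value with 12, 20 and 45 levels (about 5.4%, 5.3-5.5% and 5.7%). That is about as anticonservative as ML. Going directly to ARH(1) is not safe either: its model-based standard error was off by about −4% to +8% in further runs. ARH(1) and AR(1) make correlation decay as a power of visit index, whereas Table 3 puts the TMS visits at weeks 4, 13, 26 and 52, with gaps of 9, 13 and 26 weeks.

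**The case against.** The strongest reply is that the harm needs an event that will probably not occur. Ten covariance parameters from about 300 patients should be estimable by REML, and if REML converges the rule is never used. That stands, and it limits the point to a contingency.

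Second, the higher figures assume almost no pooling. About 300/51 ≈ 6 patients per centre, or 2 per arm, makes substantial pooling plausible, so the 12-20 level figures are the more realistic. The pooled count is left to the SAP. This stands too.

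Third, no single simulated rejection rate settles the matter: Monte Carlo error is roughly 0.3 to 0.5 points, and one ML rate was below 5%. That is fair. The sizes quoted here come from the standard-error ratio, and the paired runs support the direction.

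Fourth, trying ML first preserves the unstructured matrix, and a 1-2% error may be smaller than the error from a wrong simpler structure. This is a sound argument against jumping from REML to ARH(1). It is no argument against retrying unstructured REML first, which gives up nothing.

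A reader might infer that the secondary repeated-measures models, which inherit the ladder, are more likely to need it. The documents do not support that. HD-CAB total, CIBIC-Plus and TFC are evaluated after baseline only at Months 6 and 12 (section 9.6.1.2), so their unstructured matrix has three parameters rather than ten. Caudate volume is an ANCOVA and does not use the ladder.

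**Conclusion.** The point holds as a small, conditional fault. If unstructured REML does not converge for TMS, the prescribed switch to ML understates Month 12 standard errors by about 1-2% with 12-20 pooled centre levels (level about 5.3-5.4% per comparison), and by about 3.5% if almost no centres are pooled (about 5.9%).

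These figures assume 300 patients, two-sided testing and the correlation and dropout patterns listed above. The number of pooled levels is the main unknown.

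A reader might infer that the trial's claimed 5% error rate is undermined. The documents do not support that: REML is the default, its failure is unlikely for this endpoint, and the excess if it fails is a few tenths of a point, at most about 0.9. The rule is worth correcting because correcting it costs nothing.

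**What to change.** In section 9.6.2.1 and the matching Synopsis paragraph, replace the ML step and restate the ladder:

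1. On non-convergence, refit the unstructured REML model with Fisher scoring and improved starting values.
2. Leave the unstructured matrix only if that fails, and keep REML for every later structure.
3. Begin the later structures with heterogeneous Toeplitz, which does not force correlation to decay as a power of visit index.
4. Name the degrees-of-freedom method, for example Kenward-Roger.
5. If sandwich standard errors are used for a fit that is not unstructured, use a small-sample bias-corrected version.

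The secondary and exploratory models inherit the change by reference. The cost is a few lines of text settled before unblinding, with no extra data, patients or time.

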As the intention is to investigate laquinimod as a treatment with the potential to slow disease progression and prohibit neuronal death in the CNS, the study should also be sized to be able to detect changes in brain atrophy rate after treatment with laquinimod. One of the most sensitive measures to detect brain atrophy over time in patients with HD is change in the caudate volume. It is estimated that approximately 100 patients per arm will also enable a power of 80% to detect a beneficial effect of 0.95 (30% of the estimated decline in placebo) or more in the percent change from baseline in caudate brain atrophy of an active laquinimod arm compared to placebo, assuming SD of 2.36 and type I error of 5%.

Statistical Analyses

Due to the decision from 10 January 2016 to discontinue treatment of the laquinimod 1.5 mg dose arm, and the low number of enrolled patients compared to the target at this time, data from the laquinimod 1.5 mg treatment arm will be presented descriptively only, and will not be included in any inferential analyses for efficacy or safety.

Control of Type I Error Rate

The Hochberg's Step-Up method for multiple comparisons between treatment arms in combination with the hierarchical method between the primary efficacy endpoint and the secondary efficacy endpoints, will be used to maintain the experiment wise type I error of 5% level.

Primary Efficacy Endpoint Analysis

The change from baseline in UHDRS-TMS will be analyzed using a Repeated Measures model (SAS® MIXED procedure with REPEATED sub-command). The model will include the following fixed effects: categorical week in trial by treatment interaction, center, and UHDRS-TMS at baseline. The unstructured covariance matrix for repeated observations within patients will be used. In case that the model will not converge, the Maximum-Likelihood (ML) estimation method will be used instead of the default Restricted ML (REML). If the model still does not converge then a simpler covariance structures with less parameters will be used, according to the following order: Heterogeneous Autoregressive(1) [ARH(1)], Heterogeneous Compound Symmetry (CSH), Autoregressive(1) [AR(1)], and Compound Symmetry (CS). The estimated means at the Month 12 visit will be compared between the active treatment arms and the placebo arm.

The Hochberg's Step-Up method for multiple comparisons between treatment arms will be used to control inflation in type I error rate.

Secondary Efficacy Endpoints Analyses

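### The covariance fallback list ends with AR(1) and CS, which force one variance on all visits; if that step is reached, and the spread of change grows towards Month 12, the Month 12 test is too liberal

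*Protocol*

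**What the plan says.** Section 9.6.2.1 of the protocol analyses change in UHDRS-TMS with a repeated-measures model. The default is clear: "The unstructured covariance matrix for repeated observations within patients will be used". The first fallback changes the estimation method: "In case that the model will not converge, the Maximum-Likelihood (ML) estimation method will be used instead of the default Restricted ML (REML"). If that also fails, simpler structures follow in a fixed order. First come "Heterogeneous Autoregressive(1) [ARH(1)], Heterogeneous Compound Symmetry (CSH"), which keep a separate variance for each visit, and then "Autoregressive(1) [AR(1)], and Compound Symmetry (CS"), which do not. The synopsis repeats the whole list: "Heterogeneous Autoregressive(1) [ARH(1)], Heterogeneous Compound Symmetry (CSH), Autoregressive(1) [AR(1)], and Compound Symmetry (CS").

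The outcome is "evaluated at baseline and Months 1, 3, 6 and 12" (Section 9.6.1.1), which gives four post-baseline visits. The tested contrast is at the Month 12/Early Termination "visit will be compared between the active treatment arms and the placebo arm". The section does not say how standard errors are computed under any of these structures.

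Section 9.6.2.2 applies the same model to HD-CAB total, TFC and CIBIC-Plus, and Section 9.6.2.3 applies it to Q-Motor. Section 9.2 sizes the trial "assuming SD of 6.2 and type I error of 5" per cent, and gives no SD by visit.

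**The concern.** AR(1) and CS estimate one variance from all visits. A model-based standard error at Month 12 then reflects roughly the average visit variance rather than the Month 12 variance. If change scores spread out over time, that average lies below the Month 12 value, so intervals are too narrow and p-values too small.

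Rising spread is plausible here. Section 1.1 says that progression varies between patients. Section 1.7 says that CAG length influences the course of the disease, and patients with 36 to 49 repeats are eligible. Patients who progress at different rates drift apart.

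Section 9.7 claims overall control at 5% through Hochberg and a hierarchy. Both take the p-values as valid and cannot repair a wrong standard error. A dose wrongly declared significant would also pass on to the secondary endpoints. Section 9.6.2.4 plans no sensitivity analysis that could expose the problem.

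**Working it through.** **Inputs from the protocol.** 100 patients per arm, difference 2.5, SD 6.2, type I error 5% (taken as two-sided), four post-baseline visits, contrast at Month 12.

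**Assumed, because the protocol does not give them.** SDs at Weeks 4, 13 and 26, the correlation between visits, the dropout rate, and model-based standard errors.

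**1. The plan's own figure.** Standard error = 6.2 × √(2/100) = 0.877. Then 2.5/0.877 = 2.851, and power = Φ(2.851 − 1.960) = 81.4%. For 80% power, n = 2 × (1.960 + 0.842)² × 6.2²/2.5² ≈ 97 per arm. The stated 80% with about 100 per arm is reproduced.

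**2. Parameters with four visits.** Unstructured: 4 × 5/2 = 10. ARH(1) and CSH: 4 variances + 1 correlation = 5 each. AR(1) and CS: 1 variance + 1 correlation = 2 each.

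**3. Actual level with complete data.** Under CS, the fitted variance tends to the mean of the four visit variances. With r = √(mean variance)/6.2, the two-sided level is 2 × [1 − Φ(1.96 r)].

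| SDs at Weeks 4/13/26/52 | Mean variance | r | Level |
|---|---|---|---|
| 6.2/6.2/6.2/6.2 | 38.44 | 1.000 | 5.0% |
| 5.2/5.5/5.8/6.2 | 32.34 | 0.917 | 7.2% |
| 4.5/5.0/5.5/6.2 | 28.49 | 0.861 | 9.2% |
| 4.0/4.5/5.2/6.2 | 25.43 | 0.813 | 11.1% |
| 7.0/6.8/6.5/6.2 | 43.98 | 1.070 | 3.6% |

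For AR(1), the closest-fitting AR(1) matrix to the same true covariance gives nearly the same result: down to 9.0% in the third row and 10.7% in the fourth. With a separate Month 12 variance (unstructured, ARH(1), CSH), r = 1 and the level is 5%.

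**4. Simulation.** Null trials with 3 × 100 patients, REML, arm-by-visit and baseline effects, centre omitted, AR-type correlation 0.7, 1000 runs per setting. Ranges cover AR(1) and CS.

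| SDs at Weeks 4/13/26/52 | No dropout | 20% random dropout |
|---|---|---|
| 6.2/6.2/6.2/6.2 | 5.2–5.3% | 4.8–5.8% |
| 5.2/5.5/5.8/6.2 | 7.0–7.1% | 7.5–8.4% |
| 4.5/5.0/5.5/6.2 | 8.9–9.1% | 10.0–10.8% |
| 3.8/4.4/5.2/6.2 | 10.8–11.1% | 11.9–12.7% |

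The Hochberg family-wise error over the three rising-SD settings was about 7 to 16%.

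**5. Two-visit endpoints (Months 6 and 12).** With two visits, unstructured, ARH(1) and CSH are the same three-parameter model, and AR(1) and CS coincide. Using the TMS scale for illustration:
- Month 6 SD 5.6: mean variance (31.36 + 38.44)/2 = 34.90, r = 0.953, level 6.2%.
- Month 6 SD 4.9: mean variance (24.01 + 38.44)/2 = 31.23, r = 0.901, level 7.7%.

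**The case against.** The strongest reply is that the trigger is remote. Unstructured under REML, unstructured under ML, ARH(1) and CSH must all fail before AR(1) is tried, and a 10-parameter matrix with about 300 patients is not demanding. The list already deals with unequal variances by putting both heterogeneous structures first. This stands, and it sets the priority.

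A reader might go further and infer that the primary test runs at 7 to 12%, or that the standard error is too small whenever AR(1) or CS is used. The protocol supports neither. It states one SD and none by visit, and with equal or falling SDs the level is 5% or lower. The calculations fit AR(1) and CS to ordinary simulated trials, not to trials in which the earlier steps failed. The excess in the plan's overall error is therefore the tabled excess weighted by a small probability that nobody has estimated. It does not follow that the Hochberg procedure as a whole is undermined. Nor does the four-visit range carry over to HD-CAB total, CIBIC-Plus and TFC.

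It can also be said that the choice of standard error is normally left to the SAP, which is not available here. That is fair, and the silence is not itself a fault. The point rests on what the protocol does fix: two equal-variance structures for a test at one visit. If the SAP attaches a robust standard error to them, the inflation calculated here no longer applies.

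**Conclusion.** The point holds conditionally and at low priority. The last two fallbacks suit a single-visit contrast poorly, because they replace the Month 12 variance with a pooled one. The conclusion rests on three conditions: the variance of change rises towards Month 12, standard errors are model-based, and every earlier step has failed to converge. The first is plausible in a progressive disease but is not stated in the protocol, the second is inferred, and the third is unlikely.

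Under those conditions, the per-comparison level for TMS and Q-Motor would be about 7% with a mild rise and about 11 to 12% with a steeper one; the upper end reflects dropout. For HD-CAB total, CIBIC-Plus and TFC it would be about 6 to 8%. The sample size calculation is unaffected.

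**What to change.** In Section 9.6.2.1 and the synopsis, keep ARH(1) and CSH as they are. Add that AR(1) or CS may be used only as a last step, and then with the empirical (sandwich) standard error for the Month 12 contrast. State that the rule also covers the endpoints analysed in the same way under Sections 9.6.2.2 and 9.6.2.3.

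The cost is one sentence in two places and one PROC MIXED option, settled before unblinding. Design, sample size and conduct do not change. There are two limits. Sandwich standard errors are slightly more variable, which is minor with about 300 patients. They also correct only the standard error: if dropout depends on earlier outcomes, a misspecified covariance can still bias the Month 12 estimate itself. Ending the list at CSH would avoid the equal-variance structures altogether, but would leave no prespecified step if CSH failed.
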